Study participants will complete the following study questionnaires: Functional Disability Inventory-Child and Adolescents Form, Symptom Intensity Questionnaire, Pain Catastrophizing Scale and Revised Child Anxiety and Depression Scale. The participant's parent will also complete the Functional Disability Inventory-Parent Form. The participant will also be asked to complete the TENS Unit Daily Recording Diary to document when the device was used. A member of the research team will review the questionnaire instructions with the study participants and will advise them that they are allowed to skip any question that they are not comfortable answering. The researcher will review the questionnaires for any missed responses and will confirm with the participant if the question(s) was intentionally skipped.

Subjects will be randomized to 2 groups: a) group 1: 15 females who will only undergo active auricular TENS unit stimulation for the 8 weeks. B) Group 2: 15 females who will undergo for the first 4 weeks sham (tactile) stimulation, and the 4 weeks of active stimulation. The active settings for the TENS unit is micro mode, pulse width: 50 millisecond (ms), a frequency of 10 Hertz (hz), and intensity at sub-sensory to minimally perceived threshold. The study investigating physician will place the first TENS unit to the participant's inner part of each ear (conchae) using a clip that is provided. The investigator will train the participant on how to place the unit at home. Subjects will be asked to use the unit for at least 1 hour, twice a day. The patient will determine what time during the day that they will utilize the unit, depending on their schedule. To document the placement and the time of day that the unit is use, a data collection form will be provided. A study team member's contact

information will also be provided if the patient has any questions or concerns. A study team member will contact the patient 2 times each month as a check in and reminder. The sham stimulation will be done with non-conductive cotton cushion applied to the electrodes and the TENS unit set at an intensity of 0.02mA. The investigator and performing research coordinator will be blinded to the stimulation mode. It is possible and permitted that the performing research coordinator will become aware of which group the subject is in when checking in on the subject.

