The participant will be asked to contact the research team if they have any complications with the device or experience any adverse events.

Week 4 – Visit 2:

Study participants will return to the TRU to complete HRV and the study questionnaires specified in section F of the protocol. The participant's pain score and blood pressure will be obtained and documented on the MD Assessment Form. Participants who were randomized to receive sham therapy during weeks 0 to 4 will receive an active device. The study investigator will instruct these patients to turn it up until they feel it, then reduce the intensity until it just disappears. They will be asked to use the unit for a minimum of 1 hour, twice a day, until they return to CHW at Week 8 – Visit 3. The patient will determine what time during the day that they will utilize the unit, depending on their schedule. To document the placement and the time of day that the unit is use, a data collection form (diary) will be provided. A study team member's contact information will also be provided if the patient has any questions or concerns.

Participants who were randomized to receive active microstimulation at Week 0 - Visit 1, will continue to receive active microstimulation until they return at Week 8 – Visit 3.

A member of the TRU who is qualified to perform phlebotomy will collect the blood samples for the analysis of cytokines and flow cytometry. The participant's pain score and blood pressure will be obtained and documented on the MD Assessment Form. The coded blood samples will be escorted by a member of the research team to [name] lab where they will be prepared and frozen for later analysis by a member of the research team and/or by [name] laboratory technologist.

Week 8 – Visit 3:

Study participants will return to the TRU where they will complete HRV, the study questionnaires specified in section F of the protocol and a blood draw for cytokines and flow cytometry. The participant's pain score and blood pressure will be obtained and documented on the MD Assessment Form. The coded blood samples will be escorted by a member of the research team to [name] lab where they will be prepared and frozen for later analysis by a member of the research team or by [name] laboratory technologist.

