1. Functional Disability Inventory (FDI) will be completed by the participant (FDI-Child and Adolescent Form) and his/her parent (FDI-Parent Form). The FDI assesses the functional status of each subject. This brief 15item instrument is widely used to assess functional disability in pediatric samples³⁵, including pediatric pain ^{36,37}. Both self- and parent proxy-reports will be used. The FDI has strong internal consistency (males $\alpha = 0.86$; females $\alpha = 0.91$), reliability, and validity³⁶. Developed and validated by Walker³⁵, the FDI measures daily functions on a 5-point Likert scale such as ambulation, recreation, capacity for social interaction, performing chores, going to school, sleep, and eating. Validated for children with chronic abdominal pain, it shows excellent test-retest reliability within 2 weeks, and moderate at 3 months. It correlates well with school-related disabilities and both the child-report and the parent-report scores correlate with abdominal pain measures and other somatic symptoms^{36,37}.

2. Symptom Intensity Questionnaire score will be used to identify the most prominent 5 complaints rated in a 10 cm Likert scale the intensity form. Patients will write in each of their top 5 most severe symptoms on the corresponding line. They will then rate the symptoms severity from none (0 cm) to worst you can possibly imagine (10 cm) by placing a vertical line on the scale.

3. The Pain Catastrophizing Scale (PCS) will be completed by the participant (PCS-C) and his/her parent (PCS-P). The PCS-C is a modification of the adult Pain Catastrophizing Scale for use in children, measures pain-related cognitions and the dimensions of helplessness, rumination and magnification. This measure has both child-report and parent-report forms³⁸.

4. The Revised Child Anxiety and Depression Scale (RCADS) assesses children grades 3 to 12 containing subscales assessing for symptoms of Separation Anxiety Disorder, Social Phobia, Generalized Anxiety Disorder, Panic Disorder, Obsessive Compulsive Disorder, and Major Depressive Disorder.

5. Participants will be asked to complete the TENS Unit Daily Recording Diary while they are participating in this study. This diary consists of three columns; Date, Time 1, Time 2. Participants will update this diary daily to note when they used the TENS unit.

Blood for cytokines and flow cytometry

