Participants will complete a urine pregnancy test at study baseline in the pTRU prior to beginning use of the TENS unit. Only participants who have a negative result will be eligible to continue with the study. Pregnancy tests will be administered by a qualified pTRU nurse.

Table of study procedures

G. RISK CATEGORY:

(1) 45 CFR 46.404 - Research not involving greater than minimal risk to the children.

H. RISKS AND THE PRECAUTIONS WHICH WILL BE TAKEN TO MINIMIZE RISK EXPOSURE

Breach of patient confidentiality is a risk to participants. All standard precautions concerning patient confidentiality will be taken. These include assigning the participants a code instead of their name and using that code to label their study documents. The research team will store the link to which code is assigned with which participant on a secure, encrypted database which only members of the IRB approved research team have access. Coded data will be entered into a REDCap database.

Coded heart rate variability (ECG) and psychological questionnaire data will be sent via encrypted email to study sub-investigator, [name], at the University of Wisconsin Milwaukee, who will perform data

analysis. A member of the research team will ensure the data does not contain any identifiable information, such as name, medical record number or dates, prior to sending it to [name]. Instead of sharing dates, we will label each with the study visit (week 0, week 4, week 8). [name] will not be privy to any PHI.

It is possible that participants may develop skin irritation or scab(s) in the conchae of the ear from using the TENS unit. This is minor and, if experienced, the participant will be advised to move the placement of the auricular clip in a slightly different location. Participants may have pain or bruising from the blood collection.

Participants may temporarily experience some redness from the adhesive on the ECG surface electrodes. This redness, if experienced, is expected to resolve within a few hours.

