Completion of questionnaires may be associated with mild distress in some participants. If parents and/or children become distressed during completion of study questionnaires, they are instructed in the consent and assent forms to inform the researchers. In turn, the researchers will notify the study investigators who will assess the distressed party, inform parents of children's distress, and provide referrals as needed and as dictated by law (e.g., suspected child abuse/neglect) to ensure patient and family safety and to address psychosocial needs.

The side effects from giving a blood sample for this project may include pain and bruising at the needle entry site. Rare complications of any venipuncture (drawing blood from a vein) include fainting, arterial puncture, peripheral nerve injury, local infection, and local blood clot. There may be other unanticipated risks, but every precaution will be taken to assure the participant's personal safety and to minimize discomfort. The person drawing the participant's blood will observe the participant for side effects. The participant will be asked to inform the study team if they experience any discomfort or feel faint.

The research team will send the coded blood samples to Eve Technologies where they will be analyzed. These samples will be labeled with the code that they study team assigns to the participants. No one at Eve Technologies will have access to any of the participant's identifying information.

Because assessment of child psychosocial functioning will be administered, the potential exists for clinically significant symptoms to be brought to light that the child or parent was not aware of previously. Any child endorsing clinically significant psychological distress or substance use problems on questionnaire-reported screening measures will be assessed by a qualified study investigator. Referrals will be provided as needed. The RCADS questionnaire will be scored within 5 business days. [name] or study sub-investigator, [name], will contact study participants and their legal guardians if their score is 70 or higher to provide referrals as needed.

I. PROVISION FOR THE PROTECTION OF PRIVACY OF SUBJECTS AND TO MAINTAIN THE CONFIDENTIALITY OF DATA

As of October 2017 the NIH has updated their policy on Certificates of Confidentiality and are automatically issuing these for eligible studies that are NIH funded. They no longer issue a paper certificate, nor only submit on request.

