- \underline{X} Data is stored on MCW secured shared drives.

Key

- HD = Hard Drive
- RS = Removable Storage (USB flash drive, CD, etc.)
- PD = Portable Device (iPod; iPhone; PDA, etc.)

J. PROVISIONS FOR MONITORING DATA TO ENSURE THE SAFETY OF SUBJECTS; AND ADDITIONAL SAFEGUARDS TO PROTECT THE RIGHTS AND WELFARE OF SUBJECTS WHO ARE LIKELY TO BE VULNERABLE

[name] will monitor the health of all patients in this study per standard clinical practice and she will also monitor protocol adherence and supervise data collection, entry, and analysis.

To protect subject's privacy interests consenting and research procedures will only be done in a private setting. Research team members will only collect necessary identified information to conduct the study and below we outline the measure in place to protect the interests of the subject. We will store all records related to the child's involvement in this research in a locked file cabinet in the GI or Neurology office. We will indicate the child's identity on these records by a code number rather than by the child's name. The information linking this number with the child's identity will be kept separate from the research records in a password protected computer database or locked file cabinet. We will keep any information obtained from this research, as confidential as possible. We will see that the child's personal results of this research study are not part of the standard medical record. We will not identify the child's family by name in any publication of the research results. If such a need arises, we will obtain the child's written permission.

After the first 5 subjects have been enrolled a report to the IRB will be submitted by the study team to address the following questions:

- Has there been pain/sensitivity when using the device and ear clips?
- Has the subject used the device incorrectly (i.e., switching off the micro current setting)?
- Have other children in the household used/played with the device (or tried to)?

K. ANTICIPATED BENEFITS ASSOCIATED WITH THE PROTOCOL TO HUMAN RESEARCH PARTICIPANTS AND SOCIETY

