If this auricular TENS unit device produces the expected results, it will: 1) provide a portable, affordable tool to decrease symptoms in FGID; 2) corroborate that increasing vagal modulation improves symptoms in FGID; and 3) if the pro-inflammatory cytokines decrease and mitochondrial bioenergetics increases, it will support the role of the vagus as an anti-inflammatory function in FGID and will expand the current understanding of the action of the vagus on the cardiac mitochondria to also the mitochondria in the blood cells.

L. STOPPING POINTS THAT WOULD NOT ALLOW THE STUDY TO CONTINUE AS PROPOSED

The stopping points for the study include the request to stop by the patient or parent/guardian as well as the inability to recruit participants or unexpected adverse events that might result in stopping the study.

M. IS THERE A DATA SAFETY MONITORING BOARD IN PLACE? WHO ARE IT'S MEMBERS? HOW OFTEN DO THEY MEET?

We will not use a DSMB for this project.

N. DESCRIBE HOW THE CONSENT AND ASSENT PROCESS WILL TAKE PLACE. INCLUDE A LIST OF APPROPRIATELY TRAINED PERSONNEL WHO WILL BE INVOLVED.

Written informed consent for participation will be obtained from parents for their child's participation. Written assent will be obtained from youth 12-13 years of age using the CHW assent form. Adolescents ages 14 and up will sign the assent line on consent form per CHW policy. Participants aged 18 years will sign the adult portion on the consent form. The study will be introduced to participants at the CHW GI clinic following their standard of care visit. Consent will be obtained by a study investigator or a member of the research team at the participant's visit to the CHW GI clinic, or at the baseline visit at the TRU prior to any study procedures. Participants will have the option of having the consent/assent document read aloud to them to facilitate understanding. Copies of signed consent/assent documents will be given to participants.

Although the MD Assessment form includes questions regarding whether the participant's various family members have been diagnosed with migraine, fibromyalgia, irritable bowel syndrome or if they are double jointed, we do not believe these various family members to be secondary subjects. The goal of collecting this information is to determine factors that may contribute to the subject responding or not to the microstimulation. For this protocol, we will only consent the child participant.

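### Device-related harms have no described route except the participant contacting the team, so they and the answers in the first-five-subject report may be under-counted

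*Combined protocol and SAP*

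**What the plan says.** - **Reporting route.** Section D, Week 0 – Visit 1 ends with: "The participant will be asked to contact the research team if they have any complications with the device or experience any adverse events". At Week 4, participants are again given contact details for questions or concerns.
- **Scheduled contacts.** Section D, Week 0 – Visit 1: "A study team member will contact the patient 2 times each month as a check in and reminder". No question about harm is attached.
- **Scheduled visits.** At Weeks 4 and 8 the text lists heart rate variability, questionnaires, a blood draw and this: "The participant's pain score and blood pressure will be obtained and documented on the MD Assessment Form". The pain score is not tied to the ear or the device, and no ear check is listed.
- **Diary.** Section F: "This diary consists of three columns; Date, Time 1, Time 2". It records use only.
- **Anticipated device harm.** Section H: "It is possible that participants may develop skin irritation or scab(s) in the conchae of the ear from using the TENS unit". No rate is given. The stated precaution is advice to shift the clip.
- **First-five report.** Section J commits the team to report to the IRB once five subjects are enrolled. One question is "Has there been pain/sensitivity when using the device and ear clips"; the others concern incorrect use and use by other children in the household. How the answers are to be obtained is not stated.
- **Stopping.** Section L includes among its stopping points "unexpected adverse events that might result in stopping the study". Section M says there is no data safety monitoring board.
- **Analysis.** Section O describes no summary of adverse events.

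**The concern.** The device is used at home by participants aged 12 to 18, so the team does not observe daily use. A route that depends on the participant making contact picks up what she recognises as a problem and thinks worth reporting. Two of the three Section J questions fit that route poorly. A participant who has switched off the micro-current setting may not know it, and a sibling handling the device may not strike her as a complication or an adverse event.

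At stake are the content of the IRB report, the information available for the adverse-event stopping point, and any account of tolerability that the pilot hands to a later trial. The Section H precaution on skin irritation also works only if the team hears of the irritation.

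**Working it through.** The plan states no adverse-event rate, capture rate or detection probability, so there is no figure to reproduce. The main check is a reading of each place where a device harm could be picked up.

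| Occasion | Started by | Harm question or record stated? |
|---|---|---|
| Participant contacts team (Section D) | Participant | Yes, but only if she makes contact |
| Twice-monthly check-in (Section D), about four over 8 weeks | Team | None stated |
| Week 4 and Week 8 visits (Section D) | Team | None stated for the device |
| Daily diary (Section F) | Participant | No; usage times only |
| First-five report (Section J) | Team | Questions set, source of answers not stated |

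The readable rows of the procedures table in Section F show no adverse-event row. That table is damaged in the text available, so little weight goes on it.

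**Illustration of size.** Let p be the true probability that a subject has device pain or sensitivity, and s the share of such cases that reach the team. Both are assumptions. The number of subjects, 5, comes from Section J. Treating subjects as independent, and assuming each has used the device long enough for the event to occur:

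P(no case reported among 5) = (1 − p·s)^5

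| Assumed p | s = 1 | s = 0.5 | s = 0.25 |
|---|---|---|---|
| 10% | 0.90^5 = 59% | 0.95^5 = 77% | 0.975^5 = 88% |
| 20% | 0.80^5 = 33% | 0.90^5 = 59% | 0.95^5 = 77% |
| 30% | 0.70^5 = 17% | 0.85^5 = 44% | 0.925^5 = 68% |
| 40% | 0.60^5 = 8% | 0.80^5 = 33% | 0.90^5 = 59% |

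The direction is the same in every row; the size depends strongly on p and s.

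**What a blank means.** Among subjects who report nothing, the share who did have the event is p(1 − s)/(1 − p·s). At p = 0.3 and s = 0.5 this is 0.15/0.85 = 18%. With full capture it is zero. Without a recorded *none*, the data cannot show which case applies.

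**The case against.** Several points on the other side stand and limit the claim.

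- **Other safety routes exist.** Section H says of blood draws: "The person drawing the participant's blood will observe the participant for side effects". The anxiety and depression scale is scored within 5 business days and acted on, and Section J has health monitored under standard clinical practice. A reader might infer that all adverse events depend on the participant making contact. The documents do not support that; the point holds for device-related events, for which none of these routes states a method.
- **A form is unseen.** The MD Assessment form is used at follow-up but is not in the documents, so an adverse-event field on it cannot be excluded. Its description in Section F covers gastrointestinal history and comorbidity.
- **The report may prompt asking.** Section J sets specific questions, and the natural reading is that the team would ask the five families. A reader might infer that the report *will* be under-counted. What the documents show is an unstated source, so under-counting is possible but not established.
- **No between-arm harm comparison is planned.** A reader might infer that the arms cannot be compared fairly on harms. The aims are heart rate variability, clinical improvement and cytokines; the reporting instruction is not arm-specific; and nothing in the text shows differential reporting.
- **Small numbers are a separate matter.** Zero events in five leaves a one-sided 95% upper limit of 1 − 0.05^(1/5) = 45% even with full capture. Better questioning would not change that limit, so it does not support this point.
- **Asking about incorrect use can unblind.** Section F describes different correct use for the two methods, so an answer may reveal the group. The fix has to deal with this.

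This is also a 30-subject pilot classed in Section G as no more than minimal risk, so the point should be kept in proportion.

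**Conclusion.** The point holds in a limited form. For device-related complications and adverse events, the only described route is participant-initiated, and the team's own scheduled contacts and visits carry no stated harm question or record. Device harms and the first-five answers may therefore be under-counted, and absence of a report cannot be distinguished from absence of harm.

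The size cannot be fixed from the documents. At an assumed 30% event rate, halving capture raises the chance of an apparently clean first-five report from 17% to 44%, a rise of 27 percentage points. At assumed rates of 10%, 20% and 40% the corresponding rises are about 18, 26 and 25 points. These figures rest on assumed event and capture rates, and on adequate exposure in all five subjects; Section J triggers the report on enrolment, which does not guarantee that exposure.

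This is a worthwhile, cheap improvement. It does not threaten the main aims.

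**What to change.** At each existing check-in and at the Week 4 and Week 8 visits, ask every participant the same short scripted questions on:

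- pain or sensitivity at the ear or from the device;
- skin irritation or scabs in the ear;
- use of the device by other children;
- incorrect use.

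Record every answer on a form, including *none*. Name that form as the source for the Section J report, and add to Section O a descriptive summary by assigned group and by period (weeks 0–4 and 4–8), since the sham group changes to active stimulation at Week 4.

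Because correct use differs between the arms, have the incorrect-use item asked or received by the independent research coordinator, who under Section F already knows the assignment. Word the other items so that they do not reveal the method in use.

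**Cost.** One short form, slightly longer contacts and more minor events on record. Some unblinding risk remains; Section D already accepts that a check-in may reveal the group to the performing coordinator. No treatment or clinical rule changes.

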Document Date: January 17, 2022

Protocol ID: 1473783

NCT Number: 04247100

PRINCIPAL INVESTIGATOR: [name]

STUDY TITLE: A pilot study of a randomized sham-control auricular TENS unit stimulation to improve symptoms through vagal modulation in pediatric functional gastrointestinal disorders

STUDY PROTOCOL and STATISTICAL ANALYSIS PLAN

A. PURPOSE OF THE STUDY

The main innovation of this application is to begin to unravel a mechanism of action of vagal auricular stimulation. The known facts are that this type of stimulation improves symptoms significantly in FGID, and that it increases vagal cardio-modulation in this context. We know separately that the vagus has strong antiinflammatory effects. However, we do not know if (a) it does so in patients with FGID and (b) if this is a potential mechanism of action for the observed benefit. This project will answer these last 2 questions, and do so in a rigorous way, since placebo effect in FGID is high¹. It is critical to include a sham (tactile sensory) arm in a blinded study context.

Positive results from this study would move the FGID field forward significantly. Potential conclusions would include that (1) the vagal stimulator inhibits the neuroinflammatory cascade, (2) if the degree of inhibition correlates highly with clinical benefit, that this is a potential mechanism for the benefit it proffers; and (3) that neuro-inflammation plays a major role in pediatric FGID, a currently open question.

B. HYPOTHESIS / SPECIFIC AIMS

The overarching hypothesis of this proposal is that auricular vagal micro-stimulation reduces pain through a vagal anti-inflammatory mechanism. The 2 aims of this proposal are (1) to confirm the known cardiovagal modulatory rise and show that clinical improvement correlates with the magnitude of this rise and (2) to determine whether stimulation reduces microinflammatory indices. Comparing 4 weeks of auricular micro-stimulation with sham we will determine whether:

- Aim 1: Cardiovagal modulation (as reflected in high frequency heart rate variability, hfHRV) increases, and correlates with clinical improvement (as reflected in the Functional Disability Inventory (FDI) and a 10 point-liker scale of the 5 worse symptoms (e.g.: abdominal pain, nausea, fatigue, headaches and generalized aches)
- **Objective 1:** To determine if the auricular microstimulator produces the expected increase in hfHRV and determine if this rise parallels evidence of clinical improvement.

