The RR-interval time series recorded by the monitor will be detected from surface ECG signals at a sample rate of 1000 Hz and will be downloaded from the devices for further processing using custom HRV analysis software. The heart rate time series will be manually reviewed and processed in segments, excluding those from variability analysis in which artefacts or gaps account for > 15% of the recording. Shorter gaps will be replaced with intervals interpolated from adjacent normal beats. Frequency-domain analysis will be performed after constructing a detrended instantaneous RR-interval time series resampled at 5 Hz by piecewise cubic Hermite interpolation. The absolute and log-transformed power spectrum densities of consecutive segments will be computed for the frequency ranges of 0.04 to 0.15 Hz, designated as low-frequency power (LF), and 0.15 to 0.4 Hz, designated as high-frequency (HF) power. HF fraction will be computed as HF / (LF + HF) in addition to the LF/HF ratio. The HF power has been shown to result predominantly from parasympathetic modulation of heart rate. Time domain HRV parameters will include the standard deviation of all normal sinus beat (NN) intervals and the square root of the mean of the sum of the squares of differences between adjacent NN intervals. In addition to the inspection of the detected RR-intervals provided by the monitor, we will scan the recordings for non-stationary conditions employing Kalman-filter and wavelet-based spectrograms. Statistical analysis will be based on standard parametric or non-parametric group comparisons, as well as correlation computations were appropriate. The agreement between detected beats and the computed parameters for timedomain and frequency-domain HRV analysis between the monitors will be examined using Bland-Altman plots and summarizing using canonical correlations.

P. FINANCIAL RELATIONSHIPS

This study is supported by the 2020 CTSI Traditional Pilot Award. Participants will receive a total stipend of \$70 for participating in this study via check (\$20 after visits 1,2 and \$30 after final visit).

Q. ADVERTISEMENTS / FLIERS

We will not use advertisements or flyers for this protocol.

R. BIBLIOGRAPHY

- 1. Hoekman, D.R., et al., *The Placebo Response in Pediatric Abdominal Pain-Related Functional Gastrointestinal Disorders: A Systematic Review and Meta-Analysis.* J Pediatr, 2017. **182**: p. 155-163.e7.

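### Manual review of the heart rate recordings is not masked to visit or questionnaire scores, which leaves the within-person hfHRV rise open to expectation

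*Combined protocol and SAP*

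**What the plan says.** Three parts of the combined protocol and SAP bear on this.

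- **Section H (risks and precautions), data transfer.** "Coded heart rate variability (ECG) and psychological questionnaire data will be sent via encrypted email to study sub-investigator", the person "who will perform data" analysis. To keep dates out of the files, the plan says: "Instead of sharing dates, we will label each with the study visit (week 0, week 4, week 8"). The purpose given is privacy. Study documents carry a participant code, so files from one participant can be linked.
- **Section O, Heart Rate Variability.** "The heart rate time series will be manually reviewed and processed in segments". A segment is left out if artefact or missing signal makes up more than 15% of the recording, and smaller gaps are filled by interpolating from neighbouring beats. The term artefact is not defined, and the person who does the review is not named.
- **Section F, Blinding methodology.** Knowledge of the assigned arm is limited to the independent research coordinator and the biostatistician. The research team is allowed to learn the initial arm at the week 4 visit.

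No section says that the manual review is done without knowledge of visit or questionnaire scores, that HRV results are locked before they are combined with other data, or that a second reader checks the editing.

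**The concern.** High-frequency power is not a pure machine readout here. Someone judges which stretches of the recording are artefact, and that judgement affects the result. Section H gives the receiving analyst the visit for each recording.

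Arm concealment does not cover this. By design every participant is untreated at week 0 and on active stimulation from week 4 to week 8, so the visit label reveals treatment status at weeks 0 and 8. Only at week 4 does concealing the arm hide it.

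Two results depend on change within a person. Section B expects hfHRV to be 10% higher at week 4 than at baseline in more than half the participants. Section C treats the second phase as an additional comparison of sham with active therapy, which brings in the sham group's change from week 4 to week 8. An editor who expects later recordings to look better could move both without intending to.

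Aim 1 also asks whether hfHRV "increases, and correlates with clinical improvement (as reflected in the Functional Disability Inventory (FDI"); the other measure named is a ten-point rating of the five worst symptoms. That link is the mechanistic claim of the trial, so it matters whether unmasked review reaches it as well.

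**Working it through.** The plan gives no SD for hfHRV, no reader-agreement figure and no power inputs, so there is no stated figure to reproduce. The calculations below show which results are exposed. They do not estimate the bias.

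**Inputs from the plan:** 15 participants per arm, 30 in all (Section D); an expected hfHRV rise of 10% by week 4 in more than half of them (Section B).

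**Assumptions not in the plan:** SD of the change in ln(HF) of 0.3 to 0.8; normal changes; two-sided 5% tests; editing shifts as shown. Simulations used 20,000 runs per setting.

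**Step 1. Visit known, same shift for everyone: the within-person rise.** With no true change, the share of participants with a rise of at least 10% is 1 − Φ(ln 1.1 / SD), where ln 1.1 = 0.095. If editing lifts every follow-up recording by 10%, the share is 1 − Φ(0) = 0.50.

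| SD of change in ln(HF) | No edit | Uniform +10% edit |
|---|---|---|
| 0.3 | 0.375 | 0.50 |
| 0.5 | 0.424 | 0.50 |
| 0.8 | 0.453 | 0.50 |

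A uniform shift of 0.5 SD takes the false-positive rate of a one-sample test of change in one arm (n = 15) from 0.05 to 0.44. That is a larger edit than 10%: 0.5 × 0.3 = 0.15 and 0.5 × 0.8 = 0.40 on the log scale, against 0.095.

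**Step 2. The same shift: the between-arm contrast.** The shift cancels. The two-sample test at 15 per arm keeps a false-positive rate of 0.048.

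**Step 3. The same shift: the correlation with improvement.** For change scores, Cov(ΔHRV + c, improvement) = Cov(ΔHRV, improvement). A constant c drops out. With a 0.5 SD shift and true correlation zero, the simulated mean r is about 0 and the false-positive rate is 0.051 at n = 30 and 0.050 at n = 15. The plan does not define the correlation further; Section B speaks of the magnitude of the rise, so change scores are the natural reading.

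**Step 4. Editing that follows improvement.** This needs an editor who sees clinical change. If editing adds b SD of HRV change per SD of improvement, the expected correlation is about b / √(1 + b²), for example 0.2 / √1.04 = 0.196.

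| b | Mean r, n = 30 | False-positive rate, n = 30 | False-positive rate, n = 15 |
|---|---|---|---|
| 0 | 0.00 | 0.048 | 0.049 |
| 0.1 | 0.10 | 0.08 | 0.06 |
| 0.2 | 0.19 | 0.18 | 0.11 |
| 0.3 | 0.28 | 0.35 | 0.18 |
| 0.5 | 0.44 | 0.72 | 0.40 |

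**Step 5. Do the documents put the editor in the position of Step 4?** Section H names a recipient who analyses the data; Section O describes a manual review without naming who does it. That these are the same person is a reasonable inference, not a statement. Section H describes the questionnaire data as psychological. Section F describes the FDI as a measure of functional status and the symptom form as intensity ratings, while the PCS and RCADS fit the word psychological better. Section D lists all four together as study questionnaires. The text neither includes the FDI and symptom scores in the transfer nor keeps them out.

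**The case against.** The strongest reply has four parts.

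- **Discretion is limited.** Section O sets a 15% threshold for exclusion and specifies the resampling. Section D has staff present at each recording to log movement and coughing, which gives a contemporaneous basis for calling artefact. This stands and narrows the scope for bias. It does not remove it, because artefact is undefined and the visit is still visible.
- **The randomised comparison is protected.** Aim 1 is introduced as a comparison with sham, and a uniform shift cancels between arms. This stands while the arm stays concealed, although Section F allows the research team to learn it at week 4. It does not help the within-person rise or the sham group's second-phase change.
- **A reader might infer that the visit label, sent with questionnaire data, could manufacture the Aim 1 correlation.** The documents do not support that. The label alone cannot do it (Step 3), and the plan does not say that the recipient edits the series or receives the FDI and symptom scores (Step 5). The correlations in Step 4 rest wholly on assumed editing.
- **Withholding questionnaires could obstruct safety follow-up.** Section H requires RCADS scoring within 5 business days and contact with families at scores of 70 or higher, and a sub-investigator may make that contact. This stands, and the fix has to leave it alone.

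**Conclusion.** The gap is real and narrow. The plan gives the analyst recordings labelled by visit, has the series edited by hand, and nowhere masks that step. The results exposed are the within-person hfHRV rise from week 0 to week 4 and the sham group's change from week 4 to week 8. The between-arm contrast is not affected by a shift common to both arms. The change-score correlation with improvement would be at risk only if the editor also saw clinical change, which the documents neither state nor exclude.

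The size of any bias cannot be derived from the documents. The figures above depend on an assumed SD, an assumed editing shift and an assumed test level. Nothing in the plan shows that editing under the Section O rules would move HF power by 10%. This is a low-cost improvement to a pilot study, not a defect that invalidates it.

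**What to change.** - **Section H.** Label each ECG file sent for HRV processing with a random recording ID in place of participant code and visit. The independent research coordinator, who already prepares the allocation envelopes, holds the key. Random IDs serve the privacy aim of removing dates equally well.
- **Section O.** State that manual review is done without knowledge of participant, visit, arm or questionnaire scores, and that edited RR series and HRV results are locked before they are merged with visit labels and questionnaire data. The movement and cough log can travel with the recording under the same ID.
- **RCADS.** Leave the safety scoring and family contact in Section H unchanged. If the same sub-investigator does both tasks, the RCADS data should not be linkable to the recording IDs.

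The cost is a few lines of protocol text and a relabelling step by someone already in the study. The downside is that merging has to wait for the HRV lock. No added visits, participants or staff are needed.
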